4.25. Follow-up titration every 7 days (\pm 2-3 days)

- Clinical assessment of the subject;
- Physical examination;
- Changes of medication regimen;

 neuroloop	Confidential	Protocol – The baroloop Study
--	---------------------	-------------------------------------

- Review and assessment of adverse events;
- Office cuff blood pressure; and
- Titration of vagal nerve stimulation should be repeated weekly to achieve up to a 20% reduction in systolic blood pressure or office BP < the age-adjusted 2018 ESC/ESH treatment target office blood pressure (OBP), whichever blood pressure achieved during stimulation is lower. The titration protocol described above should be followed each time the patient returns for adjustment of baroloop stimulation. The data from the IPG will also be downloaded at each visit for subsequent analysis.

4.26. 30-Day Follow-up Visit (+7 / -7 days)

- Clinical assessment of the subject;
- Physical examination;
- Changes of medication regimen;
- Review and assessment of adverse events;
- Office cuff blood pressure;
- Medication compliance testing;
- 24hr ABPM after observed therapy for hypertension;
- Quality of Life SF-36 questionnaire; and
- Further testing and titration of stimulation to achieve an OBP less than the age-adjusted target of hypertension treatment, as described in the titration directions.

4.27. 90-Day Follow-up Visit (+14 / -14 days)

- Clinical assessment of the subject;
- Physical examination;
- Changes of medication regimen;
- Review and assessment of adverse events;
- Office cuff blood pressure;
- Medication compliance testing;
- 24hr ABPM after observed therapy for hypertension;
- Quality of Life SF-36 questionnaire; and
- Further testing and titration of stimulation to achieve an OBP less than the age-adjusted target of hypertension treatment, as described in the titration directions

4.28. 180-Day Follow-up Visit (+14 / -14 days)

- Clinical assessment of the subject;
- Physical examination;
- Changes of medication regimen;

 neuroloop	Confidential	Protocol – The baroloop Study
--	---------------------	-------------------------------------

- Review and assessment of adverse events;
- Office cuff blood pressure;
- Medication compliance testing;
- 24hr ABPM after observed therapy for hypertension;
- Quality of Life SF-36 questionnaire; and
- Further testing and titration of stimulation to achieve an OBP less than the age-adjusted target of hypertension treatment, as described in the titration directions

4.29. 365-Day Follow-up Visit (+14 / -14 days)

- Clinical assessment of the subject;
- Physical examination;
- Changes of medication regimen;
- Review and assessment of adverse events;
- Office cuff blood pressure;
- Medication compliance testing;
- 24hr ABPM after observed therapy for hypertension;
- Quality of Life SF-36 questionnaire; and
- Further testing and titration of stimulation to achieve an OBP less than the age-adjusted target of hypertension treatment, as described in the titration directions

4.30. Long Term Follow-up Visits – 18 and 24-Month Follow-up Visit (+14 / -14 days)

- Clinical assessment of the subject;
- Physical examination;
- Changes of medication regimen;
- Review and assessment of adverse events;
- Office cuff blood pressure;
- Medication compliance testing;
- 24hr ABPM after observed therapy for hypertension;
- Quality of Life SF-36 questionnaire; and
- Further testing and titration of stimulation to achieve n OBP less than the age-adjusted target of hypertension treatment, as described in the titration directions

4.31. Unscheduled Follow-up Visit

If an unscheduled follow-up visit is required, the study subject should be assessed for new or unresolved adverse events. Any testing required, including imaging studies, should be provided to the study Sponsor for DSMB adjudication. Office cuff blood pressure will be taken

and will be reviewed. Change of medications, diagnostic test results, or interventions should be documented.

4.32. 4.32 Schedule of Study Visits and Assessments

Table 3: Schedule of Study Visits and Assessments

Visit	Follow-up									Long Term Follow-up
	Visit 1	Visit 2	Visit Procedure	Discharge	14 Days (+/- 3 days)	Weekly Office visits (1x/2x)*	30 Days (+/- 7 days)	90 Days (+/- 14 days)	180 Days (+/- 14 days)	
Eligibility	✓	✓	✓							
Informed Consent	✓									
Medical History	✓									
Physical Examination	✓		✓		✓		✓	✓	✓	✓
Concomitant medications	✓	✓	✓		✓		✓	✓	✓	✓
Baseline 12 lead ECG	✓									
Blood Testing	✓			✓						
24 hour ABPM		✓					✓	✓	✓	✓
Medication compliance testing		✓					✓	✓	✓	✓
Quality of Life SF-36	✓	✓					✓	✓	✓	✓
neuroloop implantation			✓							
neuroloop titration*,**					✓	(✓)	✓	✓	✓	✓
IPG recharging and data downloading*					✓	✓				
Office cuff BP Measurement	✓	✓	✓	✓	✓	✓	✓	✓	✓	✓
Discharge				✓						
Adverse Events	✓	✓	✓	✓	✓	✓	✓	✓	✓	✓

*Titration after Day 14 takes place 1x per week. The second weekly visit through Day 30 is for Office BP and IPG battery charging only. After Day 30, only one visit per week for charging and (if necessary) titration is required.

**The heart rate and blood pressure will be recorded using a Finapres device during each titration.

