After the Cuff, Pill, Lead and IPG are connected, the device must be tested. Please see the Implantation Manual and Programmer Manual for complete details of testing. Briefly, an impedance test should be performed before the IPG is placed. If impedance test is 'Passed',

place the IPG in the prepared pectoral pocket. If impedance is 'Failed', follow the steps in flow chart in the Implantation Manual to obtain a 'Passed' impedance test. After the Impedance test is passed, place the IPG in the pectoral pocket with the neuroloop logo pointing to the skin surface. Perform a 2nd impedance test. If impedance 'Passed', follow the tests. If impedance 'Failed', follow steps in Implantation Manual flow chart to obtain a 'Passed' impedance test.

Once the impedance tests have been passed, both surgical sites should be irrigated with saline before closure of each surgical incision. Incision closure should be completed with sutures in layers, and a stapler must NOT be used to close the wounds!

After wound closure, a brief 'intraoperative' stimulation test must be performed to confirm proper functioning of the neuroloop device. Please consult the Programmer Manual and Implantation Manual for detailed instructions (BL_PM_Programmer_Manual_FIH and the BL_IM_Implantation_Manual_FIH). To begin, place the Charger within its sterile cover on the implanted IPG. Use the programmer to select 'Surgery Mode' and login into the Programmer. The Charger and the IPG will connect automatically, which will be reflected on the Programmer screen. Once the 'Surgery Mode' screen appears, press the 'START STIMULATION TEST' button on the Programmer screen. The electrode that is currently being tested will be highlighted. The stimulation or pause time is displayed. The stimulation time for each electrode is 30 seconds, and the pause time between two stimulations is 30 seconds. The overall test time, if all electrodes are functional, will be 12 minutes. Once the test is finished, completion of the test is displayed in the Programmer screen. The data from the intraoperative testing may be downloaded for analysis by neuroloop.

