4.24. Stimulation Settings/Titration First-in-Human

Blood pressure titration using VNS will take several 'titration sessions' to obtain optimal control of blood pressure. The titration sessions will take place weekly after the first titration is completed 14 days after surgery until the blood pressure has reached a target value less than the age-adjusted 2018 ESC/ESH treatment target office blood pressure (OBP). In between each titration session for the first four (4) weeks, the patient will return to the hospital or office where the titration takes place to have the IPG recharged, data downloaded from the IPG, and a check of OBP. Thus, there will be two alternating types of visits each week for the first 4 weeks of titration, one for titration, data downloading from the IPG and IPG charging and one for an OBP check, data downloading from the IPG and IPG charging.

After 4 weeks, titration may be done weekly, and the IPG charging may be done weekly when the titration is conducted. The titration process will continue until the target OBP is reached or the patient's responses to VNS are sufficiently reliable to allow less frequent follow-up after each new titration of OBP. Once a stable, target OBP is reached, blood pressure follow-up may occur at an interval appropriate for blood pressure control as determined by the treating physician.

During the first titration of baroloop stimulation, the Investigator should explore as fully as possible the range of responses to different electrode positions and stimulation settings so that an optimal set of stimulation settings may be selected with full knowledge of the range of responses in each subject at each visit.

During the titration of blood pressure responses to baroloop stimulation, each subject's blood pressure should be monitored continuously using a Finapres device. The patient should be supine and blood pressure and heart rate should be recorded continuously. After stable BP and HR are observed in the patient, the titration of the VNS may begin. Blood pressure responses to specific stimulation tests should be recorded by the Finapres device, and it is also important to record the baseline blood pressure and recovery periods after stimulation to characterize each patient's response to baroloop stimulation. The blood pressure should also

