be measured using an arm cuff 60 seconds after the onset of the stimulation sequence. Each titration stimulation should last at least 2 minutes, and the arm cuff blood pressure should be measured 1 minute after the stimulation starts while the stimulation is still present, and once again 1 minute after the titration stimulation has stopped. These values establish the correlation between arm cuff blood pressure and Finapres readings, which will be useful for subsequent titration visits in each patient.

The Cuff completely surrounds the vagus, and some combinations of stimulation parameters can optimally increase the effective depth of penetration of the stimulating electric field into the vagus nerve. The IPG provides a biphasic charge-balanced stimulation to achieve cathodal activation of the vagus nerve, and the IPG has been programmed to provide specific combinations of the following stimulation parameters, so called presets, which may be selected using the Programmer:

- Amplitude in μ A
- Pulse width in μ s
- Repetition rate in Hz
- Duty cycles in ratios of ON-OFF-Sequences

Preset name	Amplitude (µA)	Pulse width (µs)	Frequency (Hz)	Duty cycle	Comment
Impedance	96	400	4 single pulses with distance of - 320µs	-	Used for impedance measurement
P1A	96	240	40	0.3	-
P1B	96	400	40	0.3	-
P1C	96	240	40	0.5	-
P1D	96	400	40	0.5	-
P2A	144	240	40	0.3	-
P2B	144	400	40	0.3	-
P2C	144	240	40	0.5	-
P2D	144	400	40	0.5	-
P3A	300	240	40	0.3	-
P3B	300	400	40	0.3	-
P3C	300	240	40	0.5	-
P3D	300	400	40	0.5	-
P4A	444	240	40	0.3	-
P4B	444	400	40	0.3	-
P4C	444	240	40	0.5	-
P4D	444	400	40	0.5	-
P5A	600	240	40	0.3	-
P5B	600	400	40	0.3	-
P5C	600	240	40	0.5	-
P5D	600	400	40	0.5	-
P6A	744	240	40	0.3	-
P6B	744	400	40	0.3	-
P6C	744	240	40	0.5	-
P6D	744	400	40	0.5	Used during Surgery Mode

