The purpose of titration is to determine which electrode(s) and which preset stimulation parameters (which deliver different levels of energy and strength of stimulation) provide an optimal blood pressure reduction at the lowest and most effect stimulation intensity. The preset collections of stimulation parameters were derived from animal studies and represent a limited range of the values tested in animals so that the minimally effective stimulation parameters determined during animal studies may be used in humans. The general strategy during the titration should be to select all individual active electrodes (inactive electrodes do not need to be tested) and deliver a low and a high intensity stimulation from among the preset stimulation sequences provided by the Sponsor to define the range of blood pressure responses possible in each patient. Thus, the presets may be used during the process of selecting an optimal dose

of baroloop stimulation, and the preset stimulation that provides an effect blood pressure reduction may be selected for therapeutic stimulation.

The immediate goal of each titration is to reduce the blood pressure slowly and modestly over a sequence of weeks. Therefore, the reduction in blood pressure should not exceed 20% of the blood pressure preceding the titration effort. Moreover, if the blood pressure at the time the patient returns for a titration visit is at or below the age-adjusted OBP target values described in the 2018 ESC/EHS Guidelines, then no additional titration need be done. If this is obtained during any one of the titration tests described above, the stimulation characteristics that achieved a blood pressure less than the age-adjusted OBP may be used as the therapeutic level of stimulation until the next follow-up visit so long as the titrated blood pressure is not lower than 80% of the baseline value just prior to the titration, and the patient has no symptoms of dizziness, orthostatic hypotension or other adverse effects.

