If a 20% reduction in baseline blood pressure is greater than the age-adjusted OBP target, then the target blood pressure should be approached in a series of incremental steps in which an intermediate target blood pressure not below 80% of the baseline blood pressure is targeted. This intermediate target blood pressure should then be maintained for a week (at least) until the next visit for further titration, when a further 20% reduction in blood pressure may be targeted so long as the patient has no symptoms of dizziness, orthostatic hypotension or other adverse effects

Once an effective set of stimulation parameters has been selected, this setting should be used for treatment until the next study visit, when the blood pressure response can be re-evaluated, and stimulation parameters may be adjusted as appropriate to reach the goal of a blood pressure less than the age-adjusted OBP target.

Once the first treatment stimulation level has been selected, the patient should be observed in the hospital for 24 hours (as noted above). The titration of blood pressure will be retested after 24 hours prior to discharge following the titration strategy described above over a more limited range of electrode combinations and preset stimulation values. If the treatment is well tolerated and no adverse effects of VNS are identified during the hospital stay, the patient may be discharged on the prescribed pattern of VNS. Patients need not be hospitalized following subsequent blood pressure/stimulation titrations so long as the patient has no symptoms of dizziness, orthostatic hypotension or other adverse effects.

It is the Sponsor's expectation that most patients will achieve an OBP less than the age-adjusted target of hypertension treatment within a small number of weekly titration sessions. If the titration process persists beyond 12 sessions (~ 3 months), it is permissible to extend the interval between titrations up to six weeks. The patient and physician may work together to achieve a titration schedule that achieves the age-adjusted target OBP as quickly as is safe.

N.B.: The IPG should be charged at every visit to the physician's office for follow-up. In the first four weeks of titration, the IPG will be recharged twice a week. After four weeks of titration, the IPG may be charged weekly when the well-being of the patient will also be assessed. There is no home charging possible in this First in Human Study.

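### From the first titration onward no standing blood pressure or ECG is scheduled, so a symptomless postural fall can pass the rule for accepting a setting, and AV block that leaves the rate unchanged goes unrecorded

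*Combined protocol and SAP*

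**What the plan says.** The ECG appears once in the schedule. Table 3 labels the row "Baseline 12 lead ECG" and ticks it at Visit 1 (the Visit 1 list in 4.19 does not repeat it). Orthostatic pressure and pulse are checked at Visit 1 under 4.19 and have no row in Table 3. Section 5.5 adds electrocardiographic monitoring while the device is being placed.

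For titration, section 4.24 states: "The patient should be supine and blood pressure and heart rate should be recorded continuously". The recording device is a Finapres, supplemented by arm-cuff readings during and after each stimulation. "Each titration stimulation should last at least 2 minutes", and a low and a high intensity are to be tried on every active electrode.

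Two conditions govern what happens next:

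- A setting that reaches the target may be kept if the pressure is no lower than 80% of the value "just prior to the titration, and the patient has no symptoms of dizziness, orthostatic hypotension or other adverse effects".
- If the target has not been reached, then at the next visit "a further 20% reduction in blood pressure may be targeted so long as the patient has no symptoms of dizziness, orthostatic hypotension"; the absence of any further adverse effect is also required.

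After the first treatment level is chosen, "the patient should be observed in the hospital for 24 hours". The titration is then retested before discharge. For the first four weeks an extra visit between titration sessions covers office pressure, data download and charging. The Day 14 and weekly lists (4.23, 4.25) also include a clinical assessment, a physical examination and office cuff pressure, with no posture stated.

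**The concern.** Safety is a primary objective of this first-in-human study. The protocol identifies both hazards itself. Section 2.5.5 reports AV block and asystole in humans at higher stimulation currents, and says that the left vagus, the side stimulated here, supplies the AV node. Section 2.5.2 accepts that the electrode may take in cardiac branches. Section 5.3 lists hypotension, syncope and arrhythmias as risks. Entry is barred for AV block of any grade, for orthostatic hypotension in the past year and for recent syncope (4.6.2, nos. 30, 6 and 17).

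The plan therefore screens these conditions out but schedules no test of whether stimulation brings them on. The gap matters most when a setting is accepted. The patient stays on at least three antihypertensive drugs, which are not to be reduced before six months (4.34), and the regimen may include doxazosin (4.6.1). Someone who feels well lying down can meet every written condition without having stood up. The DSMB's view of acceptable safety is part of the success definition in 6.1, yet it would have no scheduled on-therapy data on posture or conduction.

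**Working it through.** **1. Count of scheduled tests.** The lists in 4.19 to 4.31 were compared with the rows and footnotes of Table 3.

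| Stage | ECG | Standing or orthostatic pressure |
|---|---|---|
| Visit 1 | 1 (Table 3) | 1 (4.19) |
| Visit 2 | 0 | 0 |
| Implantation | monitoring during placement (5.5) | 0 |
| Days 14, 30, 90, 180, 365; Months 18, 24 | 0 of 7 | 0 of 7 |
| Weekly titration visits | 0 | 0 |
| 24-hour stay and retest | none specified | none specified |

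**2. What the titration records can show.** Finapres pressure and heart rate, cuff pressure, and the heart rate logged by the IPG (3.12) should reveal bradycardia, pauses and dropped beats. None is stated to record AV conduction, and none is taken standing. What is left unseen is AV block that does not alter the rate and a postural fall without symptoms.

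**3. Does the operating-room test stand in for an ECG at titration?** Section 4.22 states: "The stimulation time for each electrode is 30 seconds, and the pause time between two stimulations is 30 seconds". With 12 electrodes, 12 × (30 + 30) s = 720 s = 12 min, which reproduces the plan's stated test time; 12 × 30 s = 6 min of that is stimulation. It runs at preset P6D ("Used during Surgery Mode"), the strongest in the table, and the monitoring in 5.5 plausibly covers it. At the first titration each stimulation lasts at least 120 s, and 120 / 30 = 4 times as long. With 12 active electrodes, 12 × 2 × 2 min = 48 min; with 6 active, 6 × 2 × 2 = 24 min. No ECG is specified for any of it. Section 4.22 also says that healing alters the relation between electrode and nerve, so the earlier test does not carry over.

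**4. Pressure steps allowed.** One 20% step from a systolic pressure of 140, 160 or 180 mm Hg is 28, 32 or 36 mm Hg, leaving 112, 128 or 144. Two steps from 180 leave 0.80 × 0.80 × 180 = 115. These are ceilings on the fall measured during a supine session, not estimates of a postural fall.

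**5. Time to the next contact.** Two visits a week give 7 / 2 = 3.5 days, so about 3 to 4 days; weekly visits give about 7. Section 4.24 keeps the mid-week visit for four weeks of titration. The Table 3 footnote ends it at Day 30, which is 30 − 14 = 16 or 30 − 21 = 9 days after the first titration. If sites follow the footnote, the shorter interval ends sooner.

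**6. Sessions before the first on-therapy ABPM (Day 30 ± 7), at exact weekly spacing.**

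| First titration | ABPM Day 23 | Day 30 | Day 37 |
|---|---|---|---|
| Day 14 | 2 | 3 | 4 |
| Day 21 | 1 | 2 | 3 |

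The 24-hour retest comes on top of these. ABPM is not a standing test and is not tied to accepting a setting.

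**The case against.** The strongest reply is that several layers of cover already exist. The first setting is retested the next day, and discharge requires that treatment is tolerated with no adverse effect identified. Mid-week visits follow, and the Day 14 and weekly lists include a clinical assessment and a physical examination. The acceptance rule names orthostatic hypotension, which can be read as a measured state and not only a complaint. All of this stands as partial cover. None of it specifies either test. On the stricter reading of the rule, the condition exists but the method is missing, which leads to the same fix for standing pressure.

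A second reply is that documents not available here may already require these tests: the Implantation and Programmer Manuals, the Investigator's Brochure, the risk assessment and the investigator briefing checklist. That cannot be excluded.

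Four stronger readings are tempting, and the documents do not support them:

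- *Serious rhythm disturbance would go unseen.* Asystole or dropped beats would probably show on the records in step 2, and the human evidence in 2.5.5 does not concern this device.
- *Every accepted setting runs unobserved for a week.* The 24-hour retest and the mid-week visits contradict this for the early period.
- *Conduction information is 42 to 204 days old at first titration* (28 + 14 days; about 183 + 21 days). That describes the Visit 1 12-lead ECG alone. All entry criteria, including AV block, are reassessed on the implantation day (4.21), and there is ECG monitoring during placement.
- *Any new AV block should bar a setting.* An entry exclusion is not a stopping rule, and the documents set no grade for one.

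**Conclusion.** The point holds, and the gap is narrow. From the first titration onward the schedule contains no standing pressure and no ECG. The acceptance rule in 4.24 can be met by a patient with a symptomless postural fall, and AV block without a rate change would not be recorded. The postural part is the firmer of the two, because it bears directly on the rule for keeping or raising a setting and can be closed with equipment already in the room. The conduction part is secondary.

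The documents give no basis for estimating how often either event would occur, so the size is stated as exposure. Neither test is listed at any of the 7 named visits or at the weekly sessions, and the next contact is about 3 to 4 days away early on and about a week away later. This assumes that weekly spacing is kept and that the unseen manuals and brochure do not already require the tests. It merits an amendment, with medium confidence.

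**What to change.** **Main change (4.23, 4.24, 4.25, with a row in Table 3).** With the chosen setting on and before the patient leaves, including at the 24-hour retest, measure supine and standing cuff pressure and pulse. Do not keep the setting or take a further step if the standing fall exceeds a limit that the sponsor sets in advance, or if it causes symptoms.

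**Secondary change (4.24).** Record an ECG trace alongside the Finapres in the first titration session, and take one ECG with the chosen setting on before discharge from the 24-hour stay. The sponsor should state which grade of AV block ends use of an electrode and preset. If the Implantation or Programmer Manual already requires this, a cross-reference is enough.

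**Cost.** A protocol amendment and a few minutes per titration visit. With 12 sessions in each of 10 subjects that is 12 × 10 = 120 standing checks, plus 10 at the 24-hour retests. This is not a maximum, because 4.24 allows more than 12 sessions and later visits also include titration. About 10 ECGs are added (1 × 10), plus a trace in first sessions that are already recorded continuously. Some settings may be rejected, which could lengthen titration for those patients. No scheduled visits are added and the sample size does not change.
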